4.8. WOCBP, Contraception, Use in Pregnancy, Use in Nursing

4.8.1. Definition of Women of Childbearing Potential

WOCBP is defined as any female who has experienced menarche and who has not undergone surgical sterilization (hysterectomy or bilateral oophorectomy) and is not postmenopausal. Menopause is defined as 12 months of amenorrhea in a woman over age 45 in the absence of other biological or physiological causes. In addition, females under the age of 55 years must have a documented serum follicle stimulating hormone (FSH) level > 40mIU/mL to confirm menopause.

Females treated with hormone replacement therapy (HRT) are likely to have artificially suppressed FSH levels and may require a washout period in order to obtain a physiologic FSH level. The duration of the washout period is a function of the type of HRT used. The duration of the washout period below are suggested guidelines and the investigators should use their judgment in checking serum FSH levels.

- 1 week minimum for vaginal hormonal products (e.g., rings, creams, gels)
- 4 weeks minimum for transdermal products
- 8 week minimum for oral products

Other parenteral products may require washout periods as long as 6 months. If the serum FSH level is > 40 mIU/mL at any time during the washout period, the woman can be considered postmenopausal.

4.8.2. Contraception

One of the highly effective methods of contraception listed below is required during study duration and until the end of relevant systemic exposure, defined as 24 weeks after the end of study treatment.*

Highly Effective Contraceptive Methods That Are User Dependent
Failure rate of <1% per year when used consistently and correctly.^a

 • Combined (estrogen- and progestogen-containing) hormonal contraception associated with inhibition of ovulation^b 
 – oral – intravaginal – transdermal • Progestogen-only hormonal contraception associated with inhibition of ovulation^b 
 – oral – injectable
Highly Effective Methods That Are User Independent

 • Implantable progestogen-only hormonal contraception associated with inhibition of ovulation^b • Hormonal methods of contraception including oral contraceptive pills containing a combination of estrogen and progesterone, vaginal ring, injectables, implants and intrauterine hormone-releasing system (IUS)^c • Intrauterine device (IUD)^c • Bilateral tubal occlusion • Vasectomized partner 
A vasectomized partner is a highly effective contraception method provided that the partner is the sole male sexual partner of the WOCBP and the absence of sperm has been confirmed. If not, an additional highly effective method of contraception should be used.

- Sexual abstinence

Sexual abstinence is considered a highly effective method only if defined as refraining from heterosexual intercourse during the entire period of risk associated with the study drug. The reliability of sexual abstinence needs to be evaluated in relation to the duration of the study and the preferred and usual lifestyle of the participant.

- It is not necessary to use any other method of contraception when complete abstinence is elected.
- WOCBP participants who choose complete abstinence must continue to have pregnancy tests, as specified in **Section 9**.
- Acceptable alternate methods of highly effective contraception must be discussed in the event that the WOCBP participants chooses to forego complete abstinence

NOTES:

^a Typical use failure rates may differ from those when used consistently and correctly. Use should be consistent with local regulations regarding the use of contraceptive methods for participants participating in clinical studies.

^b Hormonal contraception may be susceptible to interaction with the study drug, which may reduce the efficacy of the contraceptive method. Hormonal contraception is permissible only when there is sufficient evidence that the IMP and other study medications will not alter hormonal exposures such that contraception would be ineffective or result in increased exposures that could be potentially hazardous. In this case, alternative methods of contraception should be utilized.

^c Intrauterine devices and intrauterine hormone releasing systems are acceptable methods of contraception in the absence of definitive drug interaction studies when hormone exposures from intrauterine devices do not alter contraception effectiveness

Unacceptable Methods of Contraception*

- Male or female condom with or without spermicide. Male and female condoms cannot be used simultaneously
- Diaphragm with spermicide
- Cervical cap with spermicide
- Vaginal Sponge with spermicide
- Progestogen-only oral hormonal contraception, where inhibition of ovulation is not the primary mechanism of action
- Periodic abstinence (calendar, symptothermal, post-ovulation methods)
- Withdrawal (coitus interruptus).
- Spermicide only
- Lactation amenorrhea method (LAM)

* Local laws and regulations may require use of alternative and/or additional contraception methods.

CONTRACEPTION GUIDANCE FOR MALE PARTICIPANTS WITH PARTNER(S) OF CHILD BEARING POTENTIAL.

Male participants with female partners of childbearing potential are eligible to participate if they agree to the following during the treatment and until the end of relevant systemic exposure.

- Inform any and all partner(s) of their participation in a clinical drug study and the need to comply with contraception instructions as directed by the investigator.
- Male participants are required to use a condom for study duration and until end of relevant systemic exposure defined as 33 weeks after the end of study treatment.
- Female partners of males participating in the study to consider use of effective methods of contraception until the end of relevant systemic exposure, defined as 7 months after the end of treatment in the male participant.
- Male participants with a pregnant or breastfeeding partner must agree to remain abstinent from penile vaginal intercourse or use a male condom during each episode of penile penetration during the treatment and until 33 weeks after the end of study treatment.

Refrain from donating sperm for the duration of the study treatment and until 7 months after the end of study treatment.

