3. PATIENT SELECTION

3.1. Eligibility Criteria

3.1.1. Age \geq 18 years.

3.1.2. ECOG performance status of 0-1 (**Appendix A**).

3.1.3. Have histologically- or cytologically-proven ductal adenocarcinoma of the pancreas.

- 3.1.4. Have metastatic disease.
- 3.1.5. Have documented radiographic disease progression at the time of study enrollment, after previous systemic chemotherapy given in a neoadjuvant, adjuvant, locally advanced or metastatic setting.
- 3.1.6. Presence of at least one lesion with measurable disease as defined by 10 mm in longest diameter for a soft tissue lesions or 15 mm in short axis for a lymph node by RECIST 1.1.
- 3.1.7. Patient's acceptance to have a tumor biopsy of an accessible lesion at baseline and on treatment.
- 3.1.8. Life expectancy of greater than 3 months.

- 3.1.9. Adequate organ and marrow function as defined below:

- Leukocytes $\geq 3,000/\text{mcL}$
- Absolute neutrophil count $\geq 1,000/\text{mcL}$
- Platelets $\geq 90 \times 10^3/\text{uL}$
- Hemoglobin $\geq 8.0 \text{ g/dL}$
- Total bilirubin ≤ 1.5 upper limit of normal (ULN) except subjects with Gilbert Syndrome, who can have total bilirubin $< 3.0 \text{ mg/dL}$
- AST(SGOT) and ALT(SGPT) $\leq 3.0 \times \text{ULN}$
- Alkaline phosphatase $\leq 5.0 \times \text{ULN}$
- Creatinine $\leq 1.5 \times \text{ULN}$ or creatinine clearance (CrCl) $\geq 40 \text{ mL/min}$ (if using the Cockcroft-Gault formula below):

$$\text{Female CrCl} = \frac{(140 - \text{age in years}) \times \text{weight in kg} \times 0.85}{72 \times \text{serum creatinine in mg/dL}}$$

$$\text{Male CrCl} = \frac{(140 - \text{age in years}) \times \text{weight in kg} \times 1.00}{72 \times \text{serum creatinine in mg/dL}}$$

- Albumin $\geq 3.0 \text{ g/dL}$

- 3.1.10. Women of childbearing potential (WOCBP) must have a negative serum pregnancy test (minimum sensitivity 25 IU/L or equivalent units of human chorionic gonadotropin [HCG]). WOCBP is defined in **Section 4.8**. NOTE: If a patient has a positive or indeterminate serum or urine pregnancy test, then an ultrasound must be done to rule out pregnancy to enroll on trial.

- WOCBP must agree to follow instructions for method(s) of contraception from the time of enrollment for the duration of treatment with study drug(s) plus 5 half-lives of study drug(s) plus 4 weeks (duration of ovulatory cycle) for a total of 5 months post treatment completion.

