- Men who are sexually active with WOCBP must agree to follow instructions for method(s) of contraception for the duration of treatment with study drug(s) plus 5 half-lives of study drug(s) plus 90 days (duration of sperm turnover) for a total of 7 months post-treatment completion.
- At least one barrier method of contraception must be employed by all sexually active patients (male and female), regardless of other methods, to prevent the transfer of body fluids.

3.1.11. Ability to understand and willingness to sign a written informed consent document.

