4.8.3. Use in Pregnancy

The investigational agents used in this protocol may have adverse effects on a fetus; therefore, women with a positive pregnancy test at screening will not be eligible for enrollment. If a subject inadvertently becomes pregnant while on treatment, the subject will immediately be removed from the study. The site will contact the subject at least monthly and document the subject's status until the pregnancy has been completed or terminated.

Pregnancy in female subjects throughout the study or within 24 weeks of completing treatment as well as any pregnancy in partners of male subjects throughout the study or within 33 weeks of completing the study should be reported initially as a serious adverse event (see SAE reporting procedures in **Section 6.5.1** and **6.5.4**) by the investigator within 24 hours of learning of its occurrence. Pregnancy information must be reported on the Pregnancy Form.

Protocol required procedures for study discontinuation and follow-up must be performed on the subject unless contraindicated by pregnancy (e.g., x-ray studies). Other appropriate pregnancy follow-up procedures should be considered if indicated.

Follow-up information regarding the course of the pregnancy, including any voluntary or spontaneous termination, perinatal and neonatal outcome and where applicable, offspring information must be reported on the Pregnancy Follow-up Form. Pregnancy outcomes must also be collected for the female partners of any males in this trial. Consent to report information regarding these pregnancy outcomes should be obtained from the female partner.

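### Section 4.8.2 gives the end of relevant systemic exposure in men as both 33 weeks and 7 months, and the sperm-donation ban stops at the shorter, about 18 days earlier

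*Combined protocol and SAP*

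**What the plan says.** Section 4.8.2 (Contraception) lists what male participants with partners of childbearing potential must agree to, during treatment and up to the end of relevant systemic exposure. The items then give these limits:

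- Condom use by the man: "until end of relevant systemic exposure defined as 33 weeks after the end of study treatment".
- Contraception by his female partner, which she is only asked to consider: "until the end of relevant systemic exposure, defined as 7 months after the end of treatment in the male participant".
- Abstinence or condom use with a pregnant or breastfeeding partner: "during the treatment and until 33 weeks after the end of study treatment".
- Sperm donation: "Refrain from donating sperm for the duration of the study treatment and until 7 months after the end of study treatment".

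For women, the same section requires highly effective contraception to an exposure end "defined as 24 weeks after the end of study treatment".

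Criterion 3.1.10 (section 3.1, Eligibility Criteria) states its durations in months. For women it is treatment "plus 5 half-lives of study drug(s) plus 4 weeks (duration of ovulatory cycle) for a total of 5 months post treatment completion". For men it is treatment "plus 5 half-lives of study drug(s) plus 90 days (duration of sperm turnover) for a total of 7 months post-treatment completion".

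**The concern.** The condom item and the female-partner item both describe drug exposure in the same man, measured from the end of his treatment. Exposure in one man cannot end at two different times, so at least one of the two figures needs correcting.

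The donation item deserves most attention because it is the only item that names donation, and it carries the shorter figure. A man who follows it to the letter may donate while another item in the same list still treats him as exposed. Section 4.8.3 states that the study agents may harm a fetus, so the date has a safety purpose. The mismatch with 3.1.10 adds to the difficulty: site staff cannot give a participant one consistent end date from the protocol.

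**Working it through.** No sample size, power or error rate is involved. The check is a unit conversion and a side-by-side comparison.

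**Inputs.** From 4.8.2: 33 weeks and 7 months for men, 24 weeks for women. From 3.1.10: 7 months for men, 5 months for women. One month is taken as 365.25/12 = 30.44 days. The calendar ranges come from counting over start dates in 2021 to 2024.

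**Men**
- 33 weeks: 33 × 7 = 231 days.
- 7 months: 7 × 365.25/12 = 213.1 days (212 to 215 by calendar).
- Difference: 231 − 213.1 = 17.9 days. By calendar it runs from 231 − 215 = 16 to 231 − 212 = 19 days.

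**Women**
- 24 weeks: 24 × 7 = 168 days.
- 5 months: 5 × 365.25/12 = 152.2 days (150 to 153 by calendar).
- Difference: 168 − 152.2 = 15.8 days. By calendar it runs from 168 − 153 = 15 to 168 − 150 = 18 days.

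**Side by side**

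| Rule | Section | Limit | Days after treatment |
|---|---|---|---|
| Condom use, men | 4.8.2 | 33 weeks | 231 |
| Pregnant or breastfeeding partner | 4.8.2 | 33 weeks | 231 |
| Female partner's contraception (advisory) | 4.8.2 | 7 months | about 213 |
| Sperm donation | 4.8.2 | 7 months | about 213 |
| Contraception, men | 3.1.10 | 7 months | about 213 |
| Contraception, women | 4.8.2 | 24 weeks | 168 |
| Contraception, women | 3.1.10 | 5 months | about 152 |

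In each comparison the month figure is the shorter one. Moving the donation and female-partner items to 33 weeks would end both on day 231 instead of about day 213.

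**The case against.** The strongest reply is that 7 months is the only male figure with a stated derivation. Criterion 3.1.10 builds it from 5 half-lives plus 90 days for sperm turnover, whereas 4.8.2 gives no derivation for 33 weeks. On that reasoning, a man who donates at 7 months is already about 90 days past 5 half-lives. This stands. It means the documents show two conflicting numbers, not a hazard at the shorter one.

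It can also be said that the lead-in to the men's list carries every item to the end of exposure, so donation is covered after all. This helps little. The lead-in rests on the very term that has two values, and the donation item states its own date, which would probably govern. In the text as read, that sentence also stands apart from the bullets, so its place in the list is not certain.

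A reader might infer more than the documents support on four points:

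- **Two different half-lives behind the two sets.** Rounding alone could explain the difference. 168/30.44 = 5.5 months and 231/30.44 = 7.6 months, which become 5 and 7 if rounded down. One half-life near 28 days would then fit both sets: (168 − 28)/5 = 28.0 days and (231 − 90)/5 = 28.2 days. Nor is the absence of a stated half-life a fault, since much of the dosing and pharmaceutical text is redacted.
- **That following 4.8.2 always satisfies 3.1.10.** This is true of duration only. Criterion 3.1.10 also requires a barrier method for all sexually active patients, while 4.8.2 asks women for one highly effective method.
- **That condom use to 33 weeks makes the partner item redundant.** The protocol nowhere says so.
- **That the pregnancy-reporting window needs the same correction.** Section 4.8.3 covers "any pregnancy in partners of male subjects throughout the study or within 33 weeks of completing the study", while 6.5.6 counts the 33 weeks from the last study drug. Moving 4.8.3 to the earlier start point would shorten a safety-reporting window as literally written, against the cautious approach taken here. Reporting to the later date meets both.

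**Conclusion.** The contradiction is real, and its severity is minor. For male participants, 4.8.2 gives the same exposure limit as 231 days and as about 213 days. The donation ban takes the shorter, ending about 18 days (16 to 19) before the longer. Criterion 3.1.10 is shorter than 4.8.2 by about 16 days for women (15 to 18) and 18 days for men (16 to 19).

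A reader might conclude that men are permitted to donate while still exposed. The documents do not establish that: they do not show which set is right.

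The reach is small. At most 39 patients are enrolled, and the gap matters only for men who consider donating between about day 213 and day 231 after treatment. The efficacy and safety analyses do not depend on it. The sizes rest only on the month-to-day conversion, and the calendar ranges bound that.

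**What to change.** As the cautious default, unless the sponsor confirms the shorter set:

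- In 4.8.2, set the sperm-donation item and the female-partner item to 33 weeks after the end of study treatment.
- In 3.1.10, set the durations to 24 weeks for women and 33 weeks for men.

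If the sponsor confirms the shorter set instead, bring the 24- and 33-week items in 4.8.2 into line with it. What matters is one figure per sex in both sections. Leave the reporting windows in 4.8.3 and 6.5.6 as they are.

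The cost is a wording amendment. A few men would go about 18 more days without donating sperm, and their partners would have about 18 more days of advisory contraception. Anyone already keeping to the other durations in 4.8.2 gains no extra contraception time.

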4.8.3. Use in Pregnancy

The investigational agents used in this protocol may have adverse effects on a fetus; therefore, women with a positive pregnancy test at screening will not be eligible for enrollment. If a subject inadvertently becomes pregnant while on treatment, the subject will immediately be removed from the study. The site will contact the subject at least monthly and document the subject's status until the pregnancy has been completed or terminated.

Pregnancy in female subjects throughout the study or within 24 weeks of completing treatment as well as any pregnancy in partners of male subjects throughout the study or within 33 weeks of completing the study should be reported initially as a serious adverse event (see SAE reporting procedures in **Section 6.5.1** and **6.5.4**) by the investigator within 24 hours of learning of its occurrence. Pregnancy information must be reported on the Pregnancy Form.

Protocol required procedures for study discontinuation and follow-up must be performed on the subject unless contraindicated by pregnancy (e.g., x-ray studies). Other appropriate pregnancy follow-up procedures should be considered if indicated.

Follow-up information regarding the course of the pregnancy, including any voluntary or spontaneous termination, perinatal and neonatal outcome and where applicable, offspring information must be reported on the Pregnancy Follow-up Form. Pregnancy outcomes must also be collected for the female partners of any males in this trial. Consent to report information regarding these pregnancy outcomes should be obtained from the female partner.

4.8.4. Use in Nursing Women

Since many drugs are excreted in human milk, and because of the potential for serious adverse reactions in the nursing infant, subjects who are breast-feeding are not eligible for enrollment.

4.9. Duration of Therapy

Subjects who are clinically stable and meet dosing requirements (per **Section 5.2**) may continue to receive treatment for up to a maximum of 2 years.

4.10. Criteria for Removal from Treatment

The reason for study removal and the date the subject was removed will be documented in the CRF. A subject must be discontinued from the trial for any of the following reasons:

- The subject or legal representative (such as parent or legal guardian) withdraws consent.

A subject must be discontinued from treatment (but may continue to be monitored in the post-treatment follow-up portion of the trial) for any of the following reasons:

- The subject or legal representative (such as a parent or legal guardian) withdraws consent for treatment,
- Disease progression as defined in **Section 4.10.1**. If there are no signs of disease stabilization after 18 weeks of therapy, subjects should be discontinued,
- Intercurrent illness that prevents further administration of treatment,
- Severe or life-threatening cemiplimab- or plerixafor-related AE(s) (see **Section 4.10.2**),
- Need for >2 dose delays due to the same related toxicity as per the dose delay guidelines (see **Section 5.2**)
- If in the opinion of the Investigator, a change or temporal or permanent discontinuation of therapy would be in the best interest of the patient,
- Noncompliance with trial treatment or procedure requirements,
- Patient is lost to follow-up,
- Patient becomes pregnant, or
- Completed 24 months of treatment with cemiplimab and plerixafor. Note: 24 months of study medication is calculated from the date of the first dose.

4.10.1. Disease Progression

Immunotherapy is expected to trigger immune-mediated responses, which require activation of the immune system prior to the observation of clinical responses. Such immune activation may take weeks to months to be evident. Some subjects may have objective volume increase of tumor lesions or other disease parameters within weeks following the start of immunotherapy. Such subjects may not have had sufficient time to

develop the required immune activation or, in some subjects, tumor volume or other disease parameter increases may represent infiltration of lymphocytes into the original tumor. In conventional studies, such tumor volume or relevant laboratory parameter increases during the first 2-4 months of the study would constitute disease progression and lead to discontinuation of imaging to detect response, thus disregarding the potential for subsequent immune-mediated clinical response [11].

Subjects will be permitted to continue with treatment beyond RECIST 1.1 defined PD as long as they meet the following criteria:

- Investigator-assessed clinical benefit, and
- Subject is tolerating study drug.

If there are no signs of disease stabilization after 18 weeks of therapy, subjects should be discontinued.

All decisions to continue treatment beyond PD must be discussed with the Protocol Chair and documented in the study records.

Tumor assessments will be made using RECIST 1.1 and iRECIST (**Appendix B and C**).

4.10.2. Cemiplimab- and Plerixafor-Related Adverse Events

Permanent discontinuation of all study treatment should be considered for any of the following (exceptions for permanent discontinuation must be approved by the Protocol Chair):

1. Severe or life-threatening related AEs, including, but not limited to, any of the following (the Protocol Chair must be notified in the event of these AEs):
 - Any grade 2 treatment-related uveitis, eye pain, or blurred vision that does not respond to topical therapy and does not improve to \leq Grade 1 severity within the re-treatment period OR requires systemic treatment
 - Any grade 3 non-skin, drug-related AE lasting > 7 days, with the following exceptions:
 - Grade 3 treatment-related uveitis, pneumonitis, bronchospasm, neurologic toxicity, hypersensitivity reaction, or infusion reaction of any duration requires discontinuation
 - Grade 3 treatment-related endocrinopathies adequately controlled with only physiologic hormone replacement do not require discontinuation
 - Grade 3 treatment-related laboratory abnormalities do not require treatment discontinuation except:

- Grade 3 treatment-related thrombocytopenia > 7 days OR that is associated with bleeding requires discontinuation
 - Any treatment-related liver function test (LFT) abnormality that meets the following criteria require discontinuation:
 - ALT or AST $> 8 \times$ ULN, regardless of duration, or
 - ALT or AST $> 5 \times$ and $\leq 8 \times$ ULN, that fails to return to \leq Grade 1 within 2 weeks despite medical intervention, or
 - Total bilirubin $> 5 \times$ ULN, or
 - Potential drug-induced liver injury (DILI) event (**Section 6.5.5**)
- Any grade 4 treatment-related AE or laboratory abnormality, except for the following events which do not require discontinuation:
 - Grade 4 neutropenia ≤ 7 days
 - Grade 4 lymphopenia and leukopenia.
 - Isolated Grade 4 amylase or lipase abnormalities that are not associated with symptoms or clinical manifestations.
 - Isolated grade 4 electrolyte imbalances/abnormalities that are not associated with clinical sequelae and are corrected with supplementation/appropriate management within 72 hours of their onset.
 - Grade 4 treatment-related endocrinopathy adverse events, such as adrenal insufficiency, ACTH deficiency, hyper- or hypothyroidism, or glucose intolerance, which resolve or are adequately controlled with physiologic hormone replacement (corticosteroids, thyroid hormones) or glucose-controlling agents, respectively, may not require discontinuation after discussion with and approval from the Protocol Chair.
- Any dosing interruption lasting > 6 weeks with the following exceptions:
 - Dosing interruptions to allow for prolonged steroid tapers to manage drug-related adverse events are allowed. Prior to re-initiating treatment in a subject with a dosing interruption lasting > 6 weeks, the Protocol Chair must be consulted. Tumor assessments should continue as per protocol even if dosing is interrupted. Periodic study visits to assess safety and laboratory studies should also continue every 6 weeks or more frequently if clinically indicated during such dosing delays.
 - Dosing interruptions > 6 weeks that occur for non-drug-related reasons may be allowed if approved by the Protocol Chair. Prior to re-initiating treatment in a subject with a dosing interruption lasting > 6 weeks, the Protocol Chair

must be consulted. Tumor assessments should continue as per protocol even if dosing is interrupted. Periodic study visits to assess safety and laboratory studies should also continue every 6 weeks or more frequently if clinically indicated during such dosing delays.

- Any AE, laboratory abnormality, or intercurrent illness which, in the judgment of the Investigator, presents a substantial clinical risk to the subject with continued dosing.

In order to standardize the management of irAEs for all subjects, treatment management algorithms can be found in the NCCN's guidelines for the management of immunotherapy-related toxicities. Additional AE treatment management guidance included in the IBs might be considered for individual cases.

